7.2 Collection and Derivation of Primary and Secondary Efficacy Assessments

Patients will have both eyes treated although only 1 eye is required to qualify based on the inclusion/exclusion criteria. For patients with only 1 qualified eye, the qualified eye will be designated as the study eye. For patients with both eyes qualified, the study eye will be the eye with the lower TBUT at the baseline (day 1) visit. For patients having both eyes qualified and the same TBUT in both eyes, the study eye will be the right eye. Efficacy analyses will be based on the data of the study eye.

7.2.1 Primary Efficacy Variable

The primary efficacy variable is complete overall ocular discomfort response at month 6. The overall ocular discomfort will be assessed on a questionnaire using a 0 to 4 scale on which 0 = none, 1 = mild, 2 = moderate, 3 = severe, and 4 = very severe. A patient with the score of 0 will be considered to be a complete overall ocular discomfort responder.

7.2.2 Secondary Efficacy Variables

There are total 8 secondary efficacy variables evaluated at month 6 as listed below.

- ***Change from Baseline in TBUT***

The change from baseline in TBUT will be analyzed as the first secondary efficacy variable. For TBUT, the mean of 3 measurements will be computed at each visit for each eye. The mean value of the study eye will be used for the analysis.

- ***Complete Blurred Vision Response***

Similar to overall ocular discomfort, blurred vision will be assessed by each patient based on a 0 to 4 scale. Proportion of patients with complete blurred vision response defined as a blurred vision score of 0 will be analyzed as a secondary efficacy variable.

- ***Complete Corneal Sodium Fluorescein Staining Response***

The complete corneal sodium fluorescein staining response is defined as a secondary efficacy variable. A responder is defined as a patient with a corneal sodium fluorescein staining score of 0 based on the Oxford scheme.

- ***Complete Ocular Burning Response***

Similar to overall ocular discomfort and blurred vision, a 0 to 4 scale will be used to assess the burning symptom experienced by patients. Proportion of patients with complete ocular burning response defined as a burning score of 0 will be analyzed as a secondary efficacy variable.

- ***Change from Baseline in Overall Ocular Discomfort Score***

In addition to the responder analysis, the change from baseline in overall ocular discomfort score will be computed and analyzed as a secondary efficacy variable.

- **≥ 1 Grade Improvement from Baseline in Overall Ocular Discomfort Score**

The proportion of patients who achieved ≥ 1 grade improvement in overall ocular discomfort score from baseline (ie, change from baseline in raw score ≤ -1) will be analyzed as a secondary efficacy variable.

- **≥ 2 Grade Improvement from Baseline in Overall Ocular Discomfort Score**

[figure not shown]
The proportion of patients who achieved ≥ 2 grade improvement from baseline (ie, change from baseline in raw overall ocular discomfort score ≤ -2) will be analyzed as a secondary efficacy variable.

[figure not shown]
- **$\geq 50\%$ Improvement from Baseline in Overall Ocular Discomfort Score**

The percent change in overall ocular discomfort score (OODS) defined as below will be computed for each patient:

$$[(OODS \text{ at month 6} - OODS \text{ at baseline})/OODS \text{ at baseline}] \times 100$$

Patients with a percent change $\leq -50\%$ (ie, improvement $\geq 50\%$) will be considered as responders and the proportion of responders will be analyzed as a secondary efficacy variable.

Approval Date: 26-Oct-2016

7.3 Hypothesis and Methods of Analysis

In general, continuous data will be summarized with descriptive statistics (number of patients, mean, standard deviation, median, minimum, and maximum) and will be analyzed using an analysis of variance (ANOVA) model or 2-sample t-test for between-group comparisons and paired t-test for within-group analyses. Categorical variables will be summarized by number of patients, frequency count, and percent, and will be analyzed using Pearson's chi-square or Fisher's exact test (if the expected cell count is less than 5 in 25% or more of the cells). Ordinal variables will be analyzed using the Cochran-Mantel-Haenszel (CMH) test or the Wilcoxon rank-sum test for between-treatment comparisons and the signed-rank test for within-treatment comparisons.

A 2-sided test with a p-value ≤ 0.05 will be considered statistically significant unless otherwise stated.

SAT and Prohibited Treatments Impacting Efficacy Assessment

Usage of SAT or prohibited treatments described below will be considered to impact the efficacy assessments for the visit immediately following the use of SAT or prohibited treatments. The subsequent visits will not be impacted, unless the SAT or prohibited treatments are used again prior to any subsequent visits within the timeframe specified below. The efficacy data that are determined to be impacted by the usage of SAT or prohibited treatment will be considered as missing for the continuous variables with the missing data imputation method described below to be implemented. For the analysis of complete response in ocular symptoms, patients will be analyzed as nonresponders for the visits impacted by SAT or prohibited treatments.

- artificial tears (including SAT): use within 24 hours before each scheduled visit (vehicle run-in visit to month 12 visit)
- lid hygiene: use at least 8 days out of the 30-day window preceding each scheduled visit or any use within 14 days before each office visit
- any use during the study after the randomization visit of oral or topical macrolides, tetracyclines, tetracycline derivative drugs

Missing Data Imputation

ITT analyses of the efficacy variables described below will use the following rules to impute the missing data:

- If the data is missing because the patient discontinued the study due to lack of efficacy or use of SAT or other prohibited treatments that impacts the efficacy assessments,
 - Responder analyses: the patient will be considered a non-responder at all subsequent visits
 - Other analyses: the missing data will be imputed using the last observation carried forward (LOCF) method
- If the data is missing because the patient discontinued the study due to reasons other than lack of efficacy, the missing data will be imputed using the LOCF method.
- The intermittent missing data will be imputed using the LOCF method.
- The missing data at baseline visit will be imputed by the mean value across all patients who had non-missing baseline assessment of the variable analyzed regardless of treatment group

[figure not shown]

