- urine pregnancy test (female patients only)
- PSA (male patients only)
- hematology, serum chemistry, and urinalysis
- vital signs

General Statistical Methods and Types of Analyses:

The primary analysis will be performed after all patients complete the month 6 visit or discontinue from the study prior to the month 6 visit. The final analysis will be performed after all patients exit the study. There will be separate database locks for the primary and final analyses.

The intent-to-treat (ITT) population comprises all randomized patients. The efficacy variables will be analyzed per the randomization schedule using the ITT population.

The per-protocol (PP) population includes all randomized and treated patients who met the key inclusion and exclusion criteria; did not use artificial tears (including SAT), lid hygiene, or other prohibited treatments that could impact the overall ocular discomfort score at month 6; and had no other major protocol deviations. The

PP population will be determined prior to database lock. The primary efficacy variables will be analyzed using the PP population on an as-treated basis.

The safety population is comprised of all patients who received at least 1 dose of study medication. All safety measures will be analyzed on an as-treated basis using the safety population.

In general, continuous data will be summarized with descriptive statistics (number of patients, mean, standard deviation, median, minimum, and maximum) and will be analyzed using an analysis of variance (ANOVA) model or 2-sample t-test for between-group comparisons, and paired t-test for within-group analyses.

Categorical variables will be summarized by number of patients, frequency count, and percent, and will be analyzed using Pearson's chi-square or Fisher's exact test (if the expected cell count is less than 5 in 25% or more of the cells). Ordinal variables will be analyzed using the Cochran-Mantel-Haenszel (CMH) test or the Wilcoxon rank-sum test for between-treatment comparisons and the signed-rank test for within-treatment comparisons. Descriptive statistics will be provided for the open-label treatment extension phase. No statistical testing will be performed for this phase.

Efficacy:

The primary and secondary efficacy analyses will be performed for the ITT population at the month 6 visit.

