6.5 Summary of Methods of Data Collection

This protocol will use electronic case report forms (eCRFs) with remote data capture through a qualified third-party vendor. Data entered into the eCRF will correspond to, and be supported by, source documentation maintained at the sites. The investigator is responsible for ensuring that data are properly recorded on each patient's eCRFs and related documents. The data will be entered on the eCRFs in a timely manner and on an ongoing basis. Site data and images will be transferred to Allergan via electronic media.

An IxRS will be used to assign patient identification numbers, randomize patients, and manage study medication inventory. Data will be transferred to Allergan on a periodic basis throughout the study.

7. Statistical Procedures

The primary efficacy analysis will be performed after all patients complete the month 6 visit or discontinue from the study prior to the month 6 visit. The final analysis will be performed after all patients exit the study. There will be separate database locks for the primary analysis and final analysis. Prior to the first database lock a detailed analysis plan (AP) will be approved.

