7.3.1 Primary Efficacy Analyses

The primary efficacy analyses will be performed for month 6 visit using the ITT population. The null hypothesis for the primary efficacy variable, complete overall ocular discomfort response, is that 0.1% AGN-195263 is no different than vehicle with respect to the proportion of patients who are complete overall ocular discomfort responders at month 6. The alternative hypothesis is that a between-group difference exists. As described above, patients who discontinued from the study due to lack of efficacy or used SAT or other prohibited treatments within the impact intervals specified will be counted as non-responders in the analysis. Missing data due to other reasons including intermittent missing visits, early discontinuation due to reasons other than lack of efficacy will be imputed by the LOCF method. The achievement of complete overall ocular discomfort response will be determined including the imputed data. The null hypothesis will be tested using the CMH method stratified by gender and baseline overall ocular discomfort score (1 vs 2 to 3). The between-group difference in the responder rate will be reported with the confidence intervals estimated based on the normal approximation for the binary variable.

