7.3.2 Secondary Efficacy Analyses

There are total 8 secondary efficacy variables. Change from baseline in TBUT described in [Section 7.2.2](#) will be analyzed using an analysis of covariance (ANCOVA) model with treatment, gender, and baseline overall ocular discomfort score (1 vs 2 to 3) as factors and the baseline TBUT value as a covariate. The complete blurred vision response, complete corneal sodium fluorescein staining response, and complete ocular burning response will be analyzed using the CMH method stratified by gender and baseline score (1 vs 2 to 3) of the corresponding variable.. In addition, there are 4 secondary efficacy variables derived based on the overall ocular discomfort score. Change from baseline in overall ocular discomfort score will be analyzed by an ANCOVA model with treatment and gender as factors and baseline overall ocular discomfort score as a covariate. The proportion of patients with ≥ 1 -grade improvement from baseline, ≥ 2 grade improvement from baseline and $\geq 50\%$ improvement from baseline in overall ocular discomfort score as defined in [Section 7.2.2](#) will be analyzed by the CMH method stratified by gender and baseline overall ocular discomfort score (1 vs 2 to 3).

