7.6 Sample Size Calculation

The total number of patients planned for this study is 527 patients including an estimated 10% attrition rate. The sample size was estimated based on the primary efficacy analysis to compare the proportion of patients with complete overall ocular discomfort response (defined as overall ocular discomfort score equals 0) at Month 6.

Based on the final analysis of an Allergan phase 2 study (protocol 195263-006), the observed proportion of patients with complete overall ocular discomfort response over a 7-day average is 20.0% vs 9.8% (between-group difference of 10.2%) for 0.1% AGN-195263 versus vehicle, respectively. A total of 237 patients per treatment group will achieve 85% power with type I error rate of 0.05 to detect a between-group difference of 10.2% in the proportion of patients with complete overall ocular discomfort response at Month 6. This is based on the two-sided z-test (pooled variance with continuity correction), as implemented in the commercial software, [REDACTED] [REDACTED] [REDACTED] [REDACTED]. Accounting for an anticipated attrition rate of 10%, enrollment of a total of 527 patients at multiple sites is planned.

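### In the visible text, the default rule of two-sided p ≤ 0.05 covers all eight month 6 secondary variables, with no gate on the primary, testing order, adjustment or nominal label

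*Combined protocol and SAP*

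**What the plan says.** - Section 7.3, default rule: "A 2-sided test with a p-value ≤ 0.05 will be considered statistically significant unless otherwise stated".
- Section 7.2.2, number of variables: "There are total 8 secondary efficacy variables evaluated at month 6 as listed below". Section 7.3.2 gives each one an ANCOVA or a stratified CMH test. They are TBUT change, three complete responses (blurred vision, corneal staining, burning) and four built on the primary score: "there are 4 secondary efficacy variables derived based on the overall ocular discomfort score".
- Section 7.2.2, the only ordering word: "The change from baseline in TBUT will be analyzed as the first secondary efficacy variable". The other seven have no rank, and nothing depends on the TBUT result.
- Section 7.3.1 states a null and an alternative for the primary only: "The null hypothesis for the primary efficacy variable, complete overall ocular discomfort response, is that 0.1% AGN-195263 is no different than vehicle". The sole efficacy hypothesis in section 2.2 and the sample size in section 7.6 also concern the primary alone.
- Protocol Summary, statistical methods, on the open-label extension: "No statistical testing will be performed for this phase". No comparable sentence is visible for the secondaries.
- Opening of section 7: "Prior to the first database lock a detailed analysis plan (AP) will be approved". That analysis plan (AP) is not among the supplied documents.

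**The concern.** Section 7.3 defines when a result counts as statistically significant and lets other text override it. For the eight secondaries no override can be seen, so each carries the full two-sided 0.05 whatever the primary shows.

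Two things follow. A secondary can be reported as significant when the primary has failed. And the chance of at least one false finding among eight tests is larger than for a single test. Section 1 describes the study as pivotal and meant to support an indication, so what may be formally claimed from the secondaries matters. Four of the eight are re-expressions of the primary score, so a significant result on one of those would not be independent confirmation of the primary.

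**Working it through.** **1. The plan's own figure.** Section 7.6 uses "20.0% vs 9.8% (between-group difference of 10.2" percentage points), two-sided 0.05 and 85% power, with pooled variance and a continuity correction. With mean rate 0.149 and d = 0.102:

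- n = [1.960·√(2·0.149·0.851) + 1.036·√(0.098·0.902 + 0.200·0.800)]² / 0.102² = 217.3 per arm
- Corrected: (217.3/4)·[1 + √(1 + 4/(217.3·0.102))]² = 236.5, rounded up to 237
- Total: 2·237/0.90 = 526.7, rounded up to 527

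Both stated figures reproduce. The sizing takes one primary test at the full 0.05. Section 7.7 plans no interim analysis, so nothing in the secondary tests touches the primary error rate.

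**2. Count of secondary tests.** 1 (TBUT) + 3 (complete responses) + 4 (discomfort-derived) = 8, which agrees with 7.2.2 and 7.3.2.

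**3. Independence as a reference only.**

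- At least one false benefit: 1 − 0.975⁸ = 18.3%
- At least one false result in either direction: 1 − 0.95⁸ = 33.7%

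These eight tests cannot be independent. Eligibility fixes the baseline discomfort score at 1, 2 or 3, and for an observed baseline the 7.2.2 definitions coincide:

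| Baseline | Events that are the same |
|---|---|
| 1 | complete response = ≥1-grade = ≥50% improvement (≥2-grade is impossible) |
| 2 | ≥1-grade = ≥50% improvement; complete response = ≥2-grade |
| 3 | ≥2-grade = ≥50% improvement |

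**4. Correlated tests.** The documents give no correlations, so a common correlation r between normal test statistics is assumed. With A(u) = Φ((1.96 − √r·u)/√(1−r)) and B(u) = A(u) − Φ((−1.96 − √r·u)/√(1−r)), and u integrated over the standard normal:

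- any false benefit = 1 − E[A⁸]
- any false result, either direction = 1 − E[B⁸]
- false secondary benefit while the primary shows no significant benefit = E[A·(1 − A⁸)], taking the primary as null too and with the same r

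| r | Benefit only | Either direction | False benefit, primary fails |
|---|---|---|---|
| 0.3 | 15.2% | 30.0% | 14.0% |
| 0.5 | 12.5% | 25.0% | 11.0% |
| 0.7 | 9.5% | 19.1% | 7.6% |
| 0.9 | 6.0% | 11.9% | 3.7% |
| One test | 2.5% | 5.0% | – |

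**5. Would a gate alone be enough?** If the primary is null, a gate limits false secondary claims to the primary's own error. If the discomfort effect is real, the gate usually opens. The four variables not derived from discomfort are then still tested unadjusted. With all four null, and before allowing for the gate, the same formula with four tests gives 17.4% in either direction at r = 0.3 and 9.4% at r = 0.9. A rule within the family is needed as well. Holm tests the smallest p-value at 0.05/8 = 0.00625, the next at 0.05/7 = 0.00714, and so on up to 0.05, stopping at the first failure.

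**The case against.** The strongest reply is that the section 7.3 sentence is general methods language, and that the plan centres its inference on the primary: section 2.2 gives one efficacy hypothesis, 7.3.1 one null and alternative, and 7.6 sizes on the primary alone. On that reading the secondaries are supportive. The open-label sentence is weak evidence to the contrary, since that phase has no control arm. This is a fair reading of intent, but no visible sentence calls the secondaries supportive or nominal, and the rule as written calls p ≤ 0.05 significant for them.

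The second reply is that the rule may sit elsewhere. The AP is a normal place for it. Sections 7.2.3 and 7.3.3 are in the table of contents but not in the visible body, there is a gap just before 7.3.1, and the reference list holds a multiple-imputation source that no visible text cites. This stands, and it limits the point to what can be read. The visible 7.3.2 does read as complete.

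A reader might take TBUT being named first as a declared hierarchy. It ranks one variable out of eight and attaches no testing consequence, so it is not a testing order.

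**Conclusion.** The point holds for the visible text, with medium confidence: eight secondary tests fall under an unqualified two-sided 0.05 rule. If no secondary has a true effect, the chance of at least one false significant benefit is about 6 to 15%, and about 12 to 30% in either direction, against 2.5% and 5% for a single test. These ranges rest on an assumed common correlation of 0.9 to 0.3.

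Three stronger conclusions might be inferred, and the documents support none of them:

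- *The plan has no multiplicity rule.* The AP was not supplied and some statistical text is not visible, so only absence from the visible text can be stated.
- *The trial's type I error is inflated.* The primary is one comparison with no interim look, and its error rate is unaffected.
- *The error across the secondaries is one in three.* The 33.7% figure needs independence, which the overlapping definitions rule out.

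Nor do the documents show that the sponsor intends to claim a secondary after a failed primary. They only leave that open.

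**What to change.** Add to section 7.3.2, and match in the AP before the first database lock:

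> Secondary variables will be tested formally only if the primary is significant at two-sided 0.05. The eight secondary tests will then be adjusted by the Holm procedure at two-sided 0.05. Otherwise their p-values are nominal.

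A fixed sequence after the same gate is an acceptable alternative, provided that the sponsor writes out all eight positions deliberately. The listing order in 7.2.2 should not be adopted by default. It places the four variables not derived from discomfort ahead of the four that are, so a failure on any of the first four would end formal testing before a discomfort-derived variable is reached. If the AP already holds a rule, state that rule in 7.3.2 so that the two agree.

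The cost is one paragraph and matching AP text. Fewer secondaries can be formally claimed: under Holm the smallest p-value must reach 0.00625 instead of 0.05. The 237 per arm, the total of 527 and the primary alpha do not change.

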2.2 Clinical Hypotheses

One drop of 0.1% AGN-195263 administered twice daily to each eye:

- Is more effective than vehicle as measured by the proportion of patients with complete overall ocular discomfort response at month 6
- Has an acceptable safety profile throughout the study treatment duration of 12 months

3. Study Design

This is a multicenter, global, randomized, parallel-group, vehicle-controlled study with 6 months of double-masked treatment followed by a 6 month open label treatment extension phase evaluating the safety, efficacy, and systemic pharmacokinetics of 0.1% AGN-195263 in patients with EDE.

Patients will be randomized to receive 0.1% AGN-195263 or its vehicle in a 1:1 ratio. The randomization will be stratified by gender and by baseline (day 1) overall ocular discomfort score (1 vs 2 to 3).

There will be up to 9 study visits including: screening (day -51), standardization (day -21), vehicle run-in (day -14), baseline (randomization, day 1), months 1, 3, 6 (primary and secondary efficacy assessments), 9, and 12/study exit (safety assessments).

The duration of the study for each patient will be up to approximately 14 months.

Use of lid hygiene (ie, warm compress, lid massage, lid scrub) or artificial tears (other than study artificial tears [SAT]) are prohibited from the standardization (day -21) visit until the end of the month 6 visit. Allergan will supply SAT (see Study Procedures Manual for further details). Starting at the standardization (day -21) visit, all eligible patients will administer SAT twice daily in each eye for 6 days. From the vehicle run-in (day -14) visit until the month 6 visit, use of SAT will be considered rescue therapy for intolerable symptoms. After the month 6 visit until the month 12/study exit visit, use of lid hygiene and/or any artificial tear product(s) will be unrestricted.

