4.5.3 Rescue Medications or Treatments

Allergan provided artificial tears (SAT, see Study Procedures Manual) may be used during the study (from the vehicle run-in (day -14) visit until the month 6 visit) only as needed as rescue medication for intolerable symptoms. In order to avoid dilution of the study medication, SAT should be instilled at least 30 minutes before or 30 minutes after each use of the study treatment.

Patients will be asked to refrain from use of SAT for 1 day prior to each study visit. "One day prior to each study visit" is defined as the morning of the day before the study visit and continues until the end of the study visit.

At each visit, patients will be asked about their use of artificial tears (SAT) by responding to the following 2 questions: 1) number of times used during the day prior to the study visit, and 2) how many times used per day on average over the week prior to the study visit.

5. Study Treatments

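### The artificial-tear impact rule reaches back to day 1, so a measured, qualifying baseline can be discarded and replaced by the mean of all patients

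*Combined protocol and SAP*

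**What the plan says.** Four statements combine.

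- **Window.** Section 7.3 flags "artificial tears (including SAT): use within 24 hours before each scheduled visit (vehicle run-in visit to month 12 visit". The visit list in Section 3 runs "vehicle run-in (day -14), baseline (randomization, day 1), months 1, 3, 6", so day 1 is a scheduled visit inside the window. The neighbouring antibiotic bullet is narrower: "any use during the study after the randomization visit of oral or topical macrolides". The tear bullet carries no such limit.
- **Consequence.** Impacted data "will be considered as missing for the continuous variables with the missing data imputation method described below to be implemented". For complete response in ocular symptoms, the patient instead counts as a non-responder at that visit.
- **Baseline rule.** "The missing data at baseline visit will be imputed by the mean value across all patients who had non-missing baseline assessment", whatever the treatment group.
- **Access to tears before day 1.** Section 4.5.3 allows the study artificial tear (SAT) from the vehicle run-in visit "only as needed as rescue medication for intolerable symptoms". Patients are asked to abstain for a day before each visit, and each visit records the "number of times used during the day prior to the study visit".

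Inclusion criteria 4 and 5 in Section 4.3 require TBUT, corneal staining and the symptom scores to qualify on day 1.

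**The concern.** At later visits there is a reason to discard a tear-influenced value: recent tear use could be mistaken for a treatment effect. At day 1 that reason is weaker, because the value precedes randomisation and any tear effect is balanced between arms in expectation.

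Because TBUT and the symptom scores must qualify on day 1, a randomised patient should normally have an observed baseline. The impact rule then becomes a main route into mean imputation. The value it removes is the one that admitted the patient. For discomfort, it is also the one that set the randomisation stratum.

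At stake are the change in TBUT (the first secondary variable), arguably the change in discomfort score, the paired within-group tests foreseen in Section 7.3, and the baseline TBUT subgroups in Section 7.4.

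**Working it through.** **Design figure first.** Section 7.6 assumes 20.0% vs 9.8%, two-sided α 0.05, pooled z-test with continuity correction. At n = 237 per arm the pooled rate is 0.149.
- Null SE = √(2 × 0.149 × 0.851 / 237) = 0.0327.
- Alternative SE = √((0.20 × 0.80 + 0.098 × 0.902) / 237) = 0.0324.
- z = (0.102 − 1/237 − 1.96 × 0.0327) / 0.0324 = 1.04, so power is 85.1%.
- 474 / 0.90 = 526.7, so 527.

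Both stated figures are reproduced, and nothing in this point changes them.

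**Individual TBUT error.** Assume entry TBUT spread evenly over the permitted 2 to 7 s.
- Pooled mean = (2 + 7)/2 = 4.5 s.
- SD of the error = 5/√12 = 1.44 s; mean absolute error = 5/4 = 1.25 s.
- A patient unchanged at 2.5 s shows 2.5 − 4.5 = −2 s; one unchanged at 6.5 s shows +2 s.
- If subgroups use the imputed baseline, every affected patient falls in the single Section 7.4 band that contains the pooled mean. Under this assumption the mean sits on the 4.5 s cut itself.

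**Group level.** Simulation with 237 per arm and 2000 runs. Assumptions: baseline uniform 2 to 7 s; month 6 value = 4.5 + 0.5 × (baseline − 4.5) + 0.5 × (active) + normal error with SD 2 s; tear use likelier at low TBUT. Each cell gives the result with observed baselines, then with mean-imputed baselines.

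| Share affected | Mean change, affected patients (s) | Mean change, active arm (s) | ANCOVA effect (s) | SE of effect (s) |
|---|---|---|---|---|
| 5% | 0.645 → −0.176 | 0.502 → 0.460 | 0.499 → 0.499 | 0.187 → 0.187 |
| 10% | 0.644 → −0.222 | 0.499 → 0.412 | 0.497 → 0.497 | 0.181 → 0.182 |
| 20% | 0.639 → −0.339 | 0.503 → 0.306 | 0.499 → 0.497 | 0.181 → 0.184 |

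The largest loss of precision is 0.184/0.181 = 1.017, just under 2%. If tear use is unrelated to TBUT, mean changes do not shift (affected patients at 20%: 0.253 → 0.251 s) and the SE goes from 0.182 to 0.185 s.

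**Responder variables, only if they use the imputed baseline.** Section 7.2.2 defines ≥1-grade improvement as "change from baseline in raw score ≤ -1". The pooled means below are assumed.
- Mean 1.9 (scores 1/2/3 in proportions 30/50/20%): all errors are losses. A true 3-to-1 patient has change 1 − 1.9 = −0.9, or −47%, and fails all three variables. A 2-to-1 patient loses ≥1-grade and ≥50%; a 3-to-2 patient loses ≥1-grade. Nobody affected can reach ≥2 grades, since 0 − 1.9 = −1.9.
- Mean 2.1 (20/50/30%): errors run both ways. A patient unchanged at 1 has 1 − 2.1 = −1.1, or −52%, and becomes a ≥1-grade and ≥50% responder; a 1-to-0 patient gains ≥2-grade. But a 3-to-1 patient still loses ≥2-grade and a 3-to-2 patient still loses ≥1-grade.

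**Share affected.** Not given. An assumed 2% to 10% of 527 is about 11 to 53 patients.

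**The case against.** **Mean imputation may not be the governing rule.** Section 7.3 also prescribes last observation carried forward, outside responder analyses, for data missing through discontinuation for lack of efficacy or use of SAT. That sentence can be parsed so that SAT use alone triggers carry-forward, and Section 8.3.3 collects TBUT and discomfort at the run-in visit. The baseline-specific rule is the more natural reading. Under either, the observed day 1 value is discarded.

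**Scope is limited to continuous variables.** This stands. The Protocol Summary speaks of TBUT change as the continuous secondary variable, in the singular. Discomfort change is analysed by ANCOVA, so including it is arguable. A reader might infer that the ≥1-grade, ≥2-grade and ≥50% variables are certainly misclassified, but nothing extends the rule to them, and the two grade definitions refer to raw scores. A reader might likewise infer that an imputed 1.9 breaks the CMH strata. Yet the analysis factor matches the categories in Table 5, fixed at randomisation, and no text says it is re-derived.

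**Such patients may be rare or ineligible.** Section 8.4 describes tear use within 24 hours of any visit as prohibited, which is firmer than a request to abstain. No visible criterion bars randomisation after such use, but several criteria are redacted, so this cannot be settled.

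**Unseen text may deal with it.** Section 7 defers detail to an analysis plan that was not supplied, and content is missing directly after the imputation rules. No claim is therefore made that sensitivity analyses are absent.

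**Discarding tear-affected baselines mirrors the month 6 rule.** That is a fair argument for consistency. But a pooled mean carries less information about the patient than a slightly tear-affected measurement.

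**Conclusion.** The point holds on the text as written. The tear rule covers day 1, and an observed baseline for a continuous variable (clearly TBUT, arguably discomfort score) is replaced by a pooled mean.

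The effect is confined to individual and within-group changes from baseline and to baseline TBUT subgroups, with an SE increase of at most about 2% at 20% affected. These sizes rest on an assumed even spread of entry TBUT, an assumed share affected and, for the shift in group means, an assumed link between tear use and low TBUT.

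Two stronger readings are not supported. The treatment comparison is not biased to any relevant degree: the imputed value precedes randomisation and ignores arm, and the simulated contrast stayed at 0.497 to 0.499 s against a true 0.5 s when tear use was linked to low TBUT. The primary endpoint is not undermined either: it is a score of 0 at month 6 and uses no change from baseline. Which baseline the responder variables and the analysis stratum use is unstated. If the responder variables take the imputed one, misclassification can go in both directions.

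**What to change.** In Section 7.3, or in the analysis plan due before the first database lock:

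- Limit the set-to-missing rule to post-randomisation visits, month 1 onward.
- State that the observed day 1 value is the baseline for every variable, including the ≥1-grade, ≥2-grade and ≥50% variables and the TBUT subgroups, and that stratified analyses use the stratum assigned at randomisation.
- Keep mean imputation only for baselines that were never collected.
- Report, per arm, how many patients used tears in the 24 hours before day 1. The visit question asks about the preceding day, so say how it maps to the 24-hour window.

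The cost is a sentence or two and one line in a table; the sample size does not change. The downside is that a few retained baselines may be slightly improved by recent tear use, balanced between arms in expectation.
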